Transcatheter Mitral Valve Repair System Early Feasibility Study Protocol

Device Name:

Dragonfly-MTM Transcatheter Mitral Valve Repair System

Version: V1.0

Date: June 8th, 2020

Protocol Synopsis

Protocol name: Dragonfly-MTM Transcatheter Mitral Valve Repair System – Early Feasibility Study Protocol

Objectives: To evaluate the safety and device performance of the Dragonfly-MTM transcatheter mitral valve repair system for the treatment of moderate-to-severe or severe mitral regurgitation in high or prohibitive surgical risk subjects. This trial is designed to study the reliability and operator performance of the Dragonfly-MTM transcatheter mitral valve repair system in an early feasibility study.

Trial products: Dragonfly-MTM Transcatheter Mitral Valve Repair System

Indications: Moderate-to-severe (3+) and severe (4+) mitral regurgitation in high or prohibitive surgical risk subjects.

Trial design: The subjects with moderate-to-severe (3^+) and severe (4^+) mitral valve regurgitation (MR) at high or prohibitive surgical risk will be evaluated by the study sites, and study eligibility confirmed by the echocardiographic core laboratory and eligibility committee. Those qualifying will then be treated with Dragonfly-MTM transcatheter mitral valve repair system after signing the informed consent. The follow-up will be conducted at discharge, 30 days, 6 months and 12 months after the operation. The primary endpoints are the incidence of major adverse events (MAE) at 30 days, and acute procedural success. Acute procedural success is defined as placement of one or more Dragonfly-MTM devices on the mitral valve with reduction of MR to 2+ or less. The secondary endpoints include all-cause mortality, cardiovascular mortality, incidence of serious adverse event, cardiovascular rehospitalization, NYHA functional class, mitral valve hemodynamics, acute technical success rate and device success rate at 6 months. Acute technical success is defined as no procedural mortality, successful in access, delivery, and retrieval of the device delivery system, and no emergency surgery or reintervention related to the device or access procedure in the catheterization laboratory. Device success is defined as no procedural mortality, proper delivery and deployment of the device, no unplanned surgical or interventional procedures related to the device, no specific device-related technical failure and or complications, function improvement of MR without significant stenosis (MR $\leq 2+$) and without associated hemolysis or thrombogenesis.

Follow-up duration: Follow-up will be conducted at discharge, 30 days, 6 months and 12 months after operation.

Inclusion criteria:

- 1. Age \geq 18 yrs
- Moderate-to-severe (3+) or severe (4+) mitral valve regurgitation on transthoracic or transesophageal echocardiography, and confirmed by echocardiographic core laboratory
- 3. The patient is on optimal guideline directed medical therapy for heart failure and remains symptomatic.
- 4. High or prohibitive surgical risk as defined by either Society for Thoracic Surgery Risk Calculator score for valve replacement ≥ 8 points; or STS score for valve repair ≥ 6 points, prohibitive risk as determined by the clinical judgement of the site heart team, including a cardiac surgeon experienced in mitral valve surgery and a cardiologist experience in mitral valve disease, due to the presence of one or more documented surgical risk factors.
- 5. Anatomically suitable for mitral valve repair and can be treated by Dragonfly-MTM confirmed by both site investigators, echocardiographic core laboratory, and the eligibility committee.
- 6. Transseptal catheterization and femoral vein access is determined to be feasible
- 7. Life expectancy ≥ 12 months
- The subject or the subject's legal representative has been informed of the nature of the trial, willing to accept the experimental tests and follow-ups, and has provided written informed consent

Exclusion criteria:

- History of heart transplantation, prior mitral valve replacement surgery. or transcatheter mitral valve procedure;
- Leaflet anatomy which may preclude Dragonfly-MTM implantation and position, as judged by the site investigators and confirmed by the echocardiographic core laboratory and eligibility committee
- 3. Evidence of calcification or significant cleft in the grasping area
- 4. LVEF < 20%
- 5. LVESD \geq 60mm;
- 6. Mobile leaflet length < 10mm

- 7. Mitral valve effective orifice area (EOA) < 3.5cm2 or in the opinion of site investigators and confirmed by the echocardiographic core laboratory and eligibility committee that mitral stenosis would result from implantation of the Dragonfly-MTM device.
- 8. Echocardiographic evidence of intracardiac mass, thrombus or vegetation;
- 9. Severe non-mitral valve disease requiring treatment .
- 10. Severe pulmonary artery hypertension (sPAP>70mmHg)
- 11. Severe right ventricular dysfunction;
- 12. Active endocarditis or previous mitral valve endocarditis; Active rheumatic heart disease or leaflets degenerated from rheumatic disease
- 13. Severe untreated coronary artery stenosis requiring revascularization; or with other cardiovascular disease requiring surgical treatment;
- 14. Extreme frailty
- 15. Hypertrophic cardiomyopathy, restrictive cardiomyopathy, constrictive pericarditis and any other structural heart disease causing heart failure other than dilated cardiomyopathy;
- 16. Renal failure requiring dialysis;
- 17. Blood cachexia including granulocytopenia (WBC < 3×109/L), acute anemia (HB < 90g/L), thrombocytopenia (PLT < 50×109/L), severe coagulopathy, and contradictions of anticoagulant and antiplatelet agents;
- 18. Evidence of an acute myocardial infarction in the prior 4 weeks;
- 19. Evidence of a shock in the prior 90 days;
- Any percutaneous cardiac intervention or carotid surgery or any cardiac surgery within the 30 days prior to randomization;
- 21. Evidence of acute peptic ulcer upper or gastrointestinal hemorrhage in the prior 90 days;
- 22. Severe symptomatic carotid artery stenosis over 70% confirmed by echocardiography;
- 23. The subjects suffer from diseases which may lead difficulty in evaluating treatment (e.g., cancer, infection, severe metabolic disease, psychosis, etc.); or special cases that were evaluated by the heart team of local experimental center as not suitable for the surgical application of this clinical trial;
- 24. Life expectancy ≤ 12 months;

- 25. Subject participating in an investigational drug or another device study within the past 1 month;
- 26. In the judgment of the investigator, subjects may not complete the trial according to poor compliance.

Primary Effectiveness Endpoint:

1) Incidence of major adverse event (MAE) at 30 days

Major adverse event is defined as one of the following components: death, myocardial infarction (MI), stroke, renal failure requiring dialysis, and cardiac surgery for Dragonfly-MTM device failure.

2) Acute procedural success

The acute procedural success is defined as successful Dragonfly-MTM implantation, and residual MR of 2+ or less at discharge. An echocardiogram at 30 days can be accepted if the discharge image was not available or hard to interpret. A death before discharge or a re-operation of mitral valve prior to 30 days is defined as acute procedure failure

Secondary Effectiveness Endpoints:

- 1. All-cause mortality (frame:6 months)
- 2. Cardiovascular mortality (frame:6 months)
- 3. Incidence of serious adverse event (SAE) (frame:6 months). If the adverse event meets any of the criteria below, it is regarded as a serious adverse event (SAE): 1) results in death;
 2) is life threatening, results in illness or injury; 3) requires inpatient hospitalization or prolongation of existing hospitalization; 4) results in a persistent or significant disability/incapacity; 5) results in a congenital anomaly/birth defect, fetal death, fetal distress; 6) results in medical or surgical intervention to prevent permanent impairment to body structure or a body function; 7) an important medical event that may not result in death, be life-threatening, or require hospitalization but may be considered serious when, based upon appropriate medical judgment, may jeopardize the patient or subject and/or may require intervention to prevent one of the outcomes listed in this definition.
- 4. Incidence of cardiovascular rehospitalization (frame:6 months)
- 5. NYHA functional class (frame:6 months)
- 6. Mitral valve hemodynamics (frame: 6 months): include residual mitral regurgitation degree, and mean mitral valve gradient.

- 7. Technical success (frame: in the catheterization laboratory): must meet all of the following items: 1) no procedural mortality; and 2) successful in access, delivery, and retrieval of the device delivery system; and 3) no emergency surgery or reintervention related to the device or access procedure.
- 8. Device success (frame: 6 months): must meet all of the following items:1) No procedural mortality; 2) Proper delivery and deployment of the device; 3) No unplanned surgical or interventional procedures related to the device; 4) No specific device-related technical failure or complication. 5) Improvement of MR without significant stenosis (MR $\leq 2+$) without associated hemolysis or thrombogenesis.

Sample size: 20 cases

Items	Screening/ Baseline	During procedure	Follow up			
			discharge	1month	6month	12months
Time frame	-14d to 0d	0	-	\pm 14d	\pm 30d	\pm 45d
Informed consent	Х					
Eligibility criteria	Х					
Medical history	Х					
Physical examination	х					
Vital signs	Х	Х	Х			
12 lead ECG	Х		Х			
Transesophageal echocardiogram	X1	х				
Transthoracic echocardiogram	X1		х	х	х	x
Complete blood count ²	х		х			
Renal function test ³	Х		Х			
CK/CK-MB / BNP	х		Х			
NYHA Functional class	х		x	х	х	x
Device performance evaluation		Х				
Medication ⁴	Х	Х	Х	х	Х	Х
Adverse events ⁵		Х	х	х	х	Х

Clinical evaluation schedule:

Note:

- 1. TTE within 45 days and TEE within 120 days prior screening frame can be accepted.
- 2. Complete blood count includes: RBC, WBC, PLT, Hb
- 3. Renal function test include serum creatinine and urea nitrogen
- 4. For medication, only anticoagulation drugs and antiplatelet drugs are recorded
- 5. Adverse events include adverse events, severe adverse events and complications.

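### The mitral regurgitation (MR) grade can qualify a subject on either TTE or TEE, but no baseline modality is fixed for the reduction that success implies, so a grade unchanged on TTE can count as acute procedural success

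*Protocol*

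**What the plan says.** **Entry.** Protocol Synopsis, Inclusion criteria, item 2, requires 3+ or 4+ "mitral valve regurgitation on transthoracic or transesophageal echocardiography, and confirmed by echocardiographic core laboratory". It gives no rule for a subject whose two modalities disagree.

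**Acute procedural success (a primary endpoint)** is defined twice.
- Trial design: "placement of one or more Dragonfly-MTM devices on the mitral valve with reduction of MR to 2+ or less". No time point, baseline modality or number of grades is given.
- Primary Effectiveness Endpoint, 2): "The acute procedural success is defined as successful Dragonfly-MTM implantation, and residual MR of 2+ or less at discharge". This is an absolute ceiling with no change from baseline. The fallback reads: "An echocardiogram at 30 days can be accepted if the discharge image was not available or hard to interpret".

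**Secondary MR outcomes.** Secondary Effectiveness Endpoints, item 6, takes the residual MR degree at 6 months. Item 8 (device success) asks, in its fifth component, for an improvement in MR with a grade of 2+ or less. Neither names a reference modality.

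**Schedule.** In the Clinical evaluation schedule, the row "Transesophageal echocardiogram" is marked at screening/baseline and during the procedure only. The row "Transthoracic echocardiogram" is marked at screening/baseline, discharge, 1, 6 and 12 months. Note 1 adds: "TTE within 45 days and TEE within 120 days prior screening frame can be accepted".

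**The concern.** A subject may enter on whichever of two readings reaches 3+, and is later graded on one of them. If the reading that let the subject in was the TEE, and the TTE was already 2+, the outcome TTE starts below the success ceiling. Success can then be recorded although the only modality measured both before and after treatment did not move.

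The resulting error favours the device, through regression to the mean and through any systematic difference between the modalities. The study has one arm, so no control group absorbs it. It reaches a primary endpoint and, through the 6-month grade, residual MR and device success. Device performance is a stated objective of the study.

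**Working it through.** **1. The text, side by side.** Take a subject with baseline TEE 3+, baseline TTE 2+ and discharge TTE 2+, device implanted.
- Inclusion item 2: met, because TEE alone suffices once the core laboratory confirms the grade.
- Primary Effectiveness Endpoint 2): met, because the residual grade is 2+.
- Trial design wording: also met if the reduction is taken from TEE 3+ to TTE 2+, which nothing in the text rules out.
- Device success, fifth component: the same holds at 6 months if the TTE grade is still 2+.

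Note 1 allows the two baseline images to be from different dates (up to 45 and up to 120 days before the screening frame), which leaves more room for disagreement.

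**2. Weight of one subject.** The sample size is 20, so one subject is 1/20 = 5 percentage points. If 18/20 = 90% (exact 95% CI 68.3% to 98.8%) included two such subjects, counting them as failures gives 16/20 = 80% (56.3% to 94.3%). Leaving them out gives 16/18 = 88.9%.

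**3. How often it might arise.** The protocol gives no disagreement rate, so this is assumed. With a share d of subjects who entered on TEE alone, the chance of at least one among 20 is 1 − (1 − d)^20: 64% for d = 5%, 88% for 10%, 98.8% for 20%.

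**4. Effect on the success rate, under an illustrative model.** All inputs are assumptions:
- True severity in screened subjects is normal, mean 3.0 to 3.2, SD 0.5 to 0.7.
- Each reading adds independent error of SD 0.3 to 0.5 grade.
- A reading of 2.5 or more counts as 3+.
- TEE reads on average the same as TTE, or 0.5 grade higher.

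Let q be the share of enrolled subjects who enter on TEE alone. The rise in the success rate compared with TTE-only entry is

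rise = q × (success rate in TEE-only entrants − success rate in TTE-qualified entrants).

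Simulation with 2,000,000 draws per setting gives q = 6% to 14% with no TEE-TTE difference and 10% to 21% with a 0.5-grade difference. With an inert device, 30% to 61% of TEE-only entrants score 2+ or less.

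| TEE relative to TTE | Rise, inert device | Rise, device lowers MR by 1.5 grades |
|---|---|---|
| No difference | 1.6 to 3.4 points | 0.5 to 2.1 points |
| 0.5 grade higher | 3.4 to 9.4 points | 0.9 to 3.3 points |

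The largest value comes from mean 3.0, SD 0.7, error 0.3 and TEE 0.5 higher: 0.185 × (0.606 − 0.097) = 0.094. With a working device the rise shrinks because most subjects succeed whichever way they entered.

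**The case against.** **The protocol does ask for a reduction.** The Trial design paragraph says so, and device success asks for improvement. A reader might infer from the endpoint section alone that the plan never requires any change; that is not so. What remains is that the detailed primary definition omits it and that no passage fixes the baseline reading.

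**Entry is screened.** The core laboratory must confirm the grade and an eligibility committee reviews the subject. The model leaves both out, so its TEE-only share need not be the trial's. But confirming a 3+ TEE does not require the TTE to agree, so such entrants are not excluded.

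**The endpoint names no modality.** True. TTE as the outcome modality is inferred from the schedule, where it is the only echocardiogram at discharge, 30 days and 6 months. The procedural TEE is not a discharge image.

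**An absolute ceiling of 2+ is a coherent choice, and a forced one-grade fall has its own bias.** Both stand. A TEE-only entrant at TTE 2+ would have to reach 1+, and if the baseline TTE under-read, a real improvement would be scored as a failure. TTE-only entry would not remove regression to the mean either: in the model, 6% to 17% of subjects still succeed with an inert device.

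**Low stakes, and perhaps a matter for the SAP.** The protocol states no performance goal or test, so no stated decision turns on one subject. A listing of TEE-only entrants could sit in a SAP, which is not shown. The conflict between two definitions of a primary endpoint, however, is in the protocol itself.

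**Conclusion.** The point holds as an inexpensive improvement, not as a flaw that invalidates the study. Entry can rest on TEE, scheduled follow-up grading is by TTE, and the reference for reduction or improvement is not fixed. An unchanged TTE grade can therefore be a success.

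The likely size is modest: about 2 to 3 points for an inert device when the modalities agree on average, up to about 9 points if TEE reads half a grade higher, and about 0.5 to 3 points if MR falls by 1.5 grades. These figures rest wholly on assumed severity, reading error and TEE-TTE difference.

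Two stronger readings are not supported. One is that a subject can succeed with no change in MR at all; the text shows only no change on TTE. The other is that 1 to 3 of 20 subjects (or 2 to 4 with a 0.5-grade difference) would be false successes. Those are the model's counts of TEE-only entrants, of whom 30% to 61% would succeed with an inert device.

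**What to change.** 1. Align Primary Effectiveness Endpoint 2) with the Trial design wording, so that both state the reduction.
2. Name the core-laboratory baseline TTE as the reference for reduction in acute procedural success and for improvement in device success. Keep the 2+ ceiling and the entry rule. For a subject with baseline TTE of 3+ or 4+, reaching 2+ is already a reduction, so the clause matters only for TEE-only entrants.
3. Report acute procedural success, device success and residual MR also on paired TTE in subjects whose baseline TTE was 3+ or 4+. List TEE-only entrants separately with both baseline grades, image dates and outcome grade, so that an improvement hidden by a low baseline TTE stays visible.

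Cost: a clause in the endpoint definitions, one additional analysis and one listing. No examination is added, because TTE is already scheduled at baseline for every subject. The additional analysis has a slightly smaller denominator, and the reported success rate may be slightly lower.

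### SAE criterion 2 is defectively worded, so the 6-month SAE incidence is not reproducibly defined and is inflated wherever the wording is applied literally

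*Protocol*

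**What the plan says.** The Protocol Synopsis, under Secondary Effectiveness Endpoints, item 3, names the incidence of serious adverse events over 6 months as an endpoint and gives the rule for counting it: "If the adverse event meets any of the criteria below, it is regarded as a serious adverse event". Seven numbered criteria follow. Criterion 2 reads in full "is life threatening, results in illness or injury".

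Three of the other criteria bear on its meaning:

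- Criterion 3: "requires inpatient hospitalization or prolongation of existing hospitalization".
- Criterion 4: "results in a persistent or significant disability/incapacity".
- Criterion 7 covers important medical events that fall outside death, life threat and hospitalization. Such an event "may be considered serious when, based upon appropriate medical judgment, may jeopardize the patient or subject".

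Note 5 to the clinical evaluation schedule describes what is recorded: "Adverse events include adverse events, severe adverse events and complications". The planned sample size is 20.

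**The concern.** Since any one criterion suffices, each must be a clear test on its own. Criterion 2 is not. If its two halves are alternatives, the second half has no threshold: a minor access-site injury or a mild infection would count as serious without being life-threatening, without a hospital stay and without lasting harm.

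Seriousness is assigned when an event is recorded, so an analysis plan would inherit the classification and could not easily repair it. If one assessor follows the letter and another the evident intent, the same event is counted differently. Evaluating safety is part of the stated objective, and the study states no hypothesis test, so the descriptive SAE rate is itself what will be reported and read.

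**Working it through.** The protocol states no adverse event or SAE rate, so there is no figure to reproduce. The check is of the wording first, then of what it can do to the rate.

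**Step 1. Possible readings of criterion 2.**

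- (a) Life-threatening, *or* results in illness or injury.
- (b) Life-threatening *and* results in illness or injury.
- (c) A garbled form of: results in a life-threatening illness or injury.

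**Step 2. Text that favours (a).** Criterion 5 of the same list uses bare commas between alternatives (congenital anomaly or birth defect, fetal death, fetal distress). Where the protocol wants a conjunction it can say so: the technical success endpoint requires all of its items and joins them with *and*.

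**Step 3. Text that favours (b) or (c).** Criterion 7 refers to events that may not involve death, life threat or hospitalization. Those are criteria 1, 2 and 3 in order, and criterion 2 is represented by life threat alone. Criteria 3, 4 and 6 each set a threshold: hospitalization, persistent or significant disability, and intervention to prevent permanent impairment. Criterion 7 asks for medical judgment. Under (a) these four criteria would have little left to do.

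**Step 4. Result of the comparison.** The context points to (b) or (c), which differ little in practice. The operative sentence does not say either, and the list's own punctuation allows (a).

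**Step 5. Effect on the endpoint.** Let pS be the share of subjects with an SAE under the narrow reading, pA the share with any adverse event, and f the share of subjects with only non-serious events who have at least one event counted as illness or injury. Then

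SAE incidence = pS + f × (pA − pS).

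Under (b) or (c), f = 0 and nothing changes. Under (a), f lies somewhere between 0 and 1. The document supplies none of pS, pA or f. The one quantity it fixes is the step size: 1/20 = 5 percentage points for each subject who moves from no SAE to at least one. A subject who already has an SAE does not move the rate.

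**Step 6. Illustration on assumed values only.** Take pS from 0.20 to 0.40 and pA from 0.60 to 0.90.

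| f | SAE incidence, lowest to highest |
|---|---|
| 0 | 0.20 to 0.40 |
| 0.5 | 0.40 to 0.65 |
| 1 | 0.60 to 0.90 |

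For example, at f = 0.5 the lowest value is 0.20 + 0.5 × (0.60 − 0.20) = 0.40 and the highest is 0.40 + 0.5 × (0.90 − 0.40) = 0.65. These figures show direction and are not estimates for this trial.

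**The case against.** The strongest reply is that no competent assessor would read criterion 2 broadly. Criterion 7 sums it up as life-threatening, and a reading that nearly empties four of seven criteria is one to reject. Note 5 also lists ordinary and severe adverse events as different things. This stands as evidence of intent, and it is why the point is put as defective wording rather than as a rule that makes ordinary events serious. It does not cure the sentence: reaching the intended meaning requires the reader to rewrite it.

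A reader might go further and infer that the SAE incidence collapses to the incidence of all adverse events. The documents do not support that. It needs reading (a), and it also needs f = 1, so that every subject with any adverse event has one that results in illness or injury. Asymptomatic laboratory, ECG or echocardiographic findings would not obviously qualify even on the literal reading.

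It is also fair that the reach is limited. This is one of eight secondary endpoints in a 20-subject early feasibility study. The MAE primary endpoint is counted from five named components, and mortality and cardiovascular rehospitalization are listed as separate endpoints. Divergence between assessors or sites is possible but not shown.

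**Conclusion.** The point holds as a defect in an operative endpoint definition. Criterion 2, combined with the rule that any one criterion suffices, permits a literal reading in which an unqualified illness or injury makes an event serious. The surrounding criteria indicate that this was not meant. The 6-month SAE incidence is therefore not reproducibly defined, and it would be overstated to the extent that the literal reading is applied.

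The size cannot be given beyond 5 percentage points per reclassified subject, taking all 20 planned subjects as the denominator. If the narrow reading is used throughout, the inflation is zero. The primary MAE endpoint is not affected.

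The use of *severe* in Note 5, where the endpoint concerns *serious* events, is a separate terminology slip. Severity and seriousness are different attributes, but Note 5 does not supply the counting rule and would not merit a point on its own.

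**What to change.** Reword criterion 2 to: *results in a life-threatening illness or injury*. Use the same wording on the adverse event form, so that the classification made at recording matches the endpoint. As a minor alignment, change *severe* to *serious* in Note 5 to the clinical evaluation schedule.

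The cost is a wording amendment and a matching form edit. No visits, data items or subjects are added. Compared with literal counting, the reported SAE rate can only fall or stay the same. Any events already classified under the present wording should be checked once against the corrected criterion.

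### Technical success, as defined in both places, counts a patient whose system is withdrawn cleanly with no device implanted as a success

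*Protocol*

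**What the plan says.** Technical success appears twice in the Protocol Synopsis. Under Trial design: "Acute technical success is defined as no procedural mortality, successful in access, delivery, and retrieval of the device delivery system", followed by a condition on emergency surgery and reintervention in the catheterization laboratory. Under Secondary Effectiveness Endpoints, item 7, it is a closed list, all of whose items must be met: no death during the procedure; "successful in access, delivery, and retrieval of the device delivery system"; and "no emergency surgery or reintervention related to the device or access procedure". The two versions agree.

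The other two success endpoints do ask for an implant:

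- Acute procedural success (primary), Trial design: "Acute procedural success is defined as placement of one or more Dragonfly-MTM devices on the mitral valve", together with a condition on mitral regurgitation (MR).
- Acute procedural success (primary), Primary Effectiveness Endpoint, item 2: "The acute procedural success is defined as successful Dragonfly-MTM implantation, and residual MR of 2+ or less at discharge".
- Device success at 6 months, Secondary Effectiveness Endpoints, item 8, second condition: "Proper delivery and deployment of the device".

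The Clinical evaluation schedule also has a row "Device performance evaluation" marked for the procedure, without stating its content. The size of the trial is given as "Sample size: 20 cases".

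**The concern.** In item 7, access, delivery and retrieval all take the delivery system as their object, not the implant. An attempt that ends with the system back outside the patient and nothing on the valve meets every condition, provided the patient survives the procedure and needs no emergency operation or reintervention.

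This matters because the Objectives say the study is meant to examine reliability and operator performance, and technical success is the only success endpoint framed in the catheterization laboratory. Failure to deploy is about as direct a sign of poor reliability or operator difficulty as this study can produce. Under the present wording it lowers the technical success rate only when accompanied by failed access, delivery or retrieval, death, or emergency surgery or reintervention. Two series with the same number of non-deployments can therefore report different rates, and a reported 100% would not tell the reader whether every patient received a device.

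**Working it through.** The protocol attaches no expected rate, goal or hypothesis to technical success, so there is no stated figure to reproduce. The check is a reading of the definitions, followed by simple proportions for scale.

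**Step 1. Apply each definition to one case.** The system is introduced, no device is deployed, the system is withdrawn, the patient is alive, and there is no emergency surgery or reintervention.

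| Endpoint | Condition that bears on the case | Result |
|---|---|---|
| Technical success (Trial design; secondary endpoint 7) | Survival; delivery system in and out; no emergency surgery or reintervention | Success |
| Acute procedural success (Trial design) | At least one device placed | Failure |
| Acute procedural success (primary endpoint 2) | Successful implantation | Failure |
| Device success (secondary endpoint 8) | Delivery and deployment of the device | Failure |

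**Step 2. Could delivery mean implantation?** Device success names delivery and deployment as two things, so in this protocol the first does not imply the second. In item 7 what is delivered is the delivery system.

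**Step 3. Size per case.** Input: n = 20 (Sample size). Each clean withdrawal adds 1/20 = 5 percentage points relative to a definition requiring deployment. The exact (Clopper-Pearson) 95% limits for x successes are the 2.5% quantile of Beta(x, n − x + 1) and the 97.5% quantile of Beta(x + 1, n − x), with the upper limit set to 100% when x = n.

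Suppose k clean withdrawals and no other failure (k is assumed):

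| k | As written | With deployment required |
|---|---|---|
| 0 | 20/20 = 100% (83.2 to 100) | 20/20 = 100% (83.2 to 100) |
| 1 | 20/20 = 100% (83.2 to 100) | 19/20 = 95% (75.1 to 99.9) |
| 2 | 20/20 = 100% (83.2 to 100) | 18/20 = 90% (68.3 to 98.8) |
| 3 | 20/20 = 100% (83.2 to 100) | 17/20 = 85% (62.1 to 96.8) |

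**Step 4. Same non-deployments, different rates.** Fix two non-deployments and no other failure, and let c of them be clean withdrawals. Successes as written = 20 − (2 − c):

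- c = 0: 18/20 = 90% (68.3 to 98.8)
- c = 1: 19/20 = 95% (75.1 to 99.9)
- c = 2: 20/20 = 100% (83.2 to 100)

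With deployment required the result is 18/20 = 90% for every c, so the gap is 0, 5 or 10 points.

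**Step 5. Could it occur in 20 patients?** The chance of at least one clean withdrawal is 1 − (1 − p)^20. The protocol gives no p, so a range is assumed: p = 2% gives 33.2%, p = 5% gives 64.2%, p = 10% gives 87.8%.

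**The case against.** The best defence is that the protocol sets up three tiers on purpose: technical success in the laboratory, acute procedural success around discharge, device success at 6 months. A first tier confined to access, handling of the delivery system and bail-out is coherent, and deployment is picked up by the other two. A patient without an implant lowers a primary endpoint, so the event cannot vanish from the results. It can also be said that successful delivery is not defined, and that an assessor might fail a case in which the device leaves the body still attached to its system. Finally, the 5 points are measured against a definition the protocol did not adopt, and the case counts are hypothetical.

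Part of this stands. The two statements of technical success do not contradict each other, a delivery-system-only tier is possible, and the consequences are limited. But the protocol nowhere says that such a tier is intended. The reading that would fail a no-implant case goes against the grammar of the item and against the separate naming of delivery and deployment in device success; if assessors might differ on it, that is itself a reason to settle the wording.

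Nor do the other endpoints isolate the event. Acute procedural success also fails for excess residual MR, death before discharge or mitral re-operation before 30 days, and device success is a five-part composite. Neither rate shows how many patients left the laboratory without a device. Nor is this a detail to leave to a statistical analysis plan, because the protocol itself fixes the rule, in two places.

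**Conclusion.** The concern holds. Followed literally, both statements of technical success count a clean withdrawal without an implant as a success, in the one success endpoint set in the catheterization laboratory of a study about reliability and operator performance. The wording conclusion rests on no assumption beyond reading the items as a complete list, which item 7 says they are.

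The overstatement is 5 percentage points per clean withdrawal at n = 20, relative to a definition requiring deployment. How many such cases would arise is unknown; if there are none, the two definitions agree. The endpoint is secondary and descriptive, with no threshold attached, so no primary result, safety count or formal decision changes. What is at risk is the meaning of the reported rate. The definition should be corrected, but it does not undermine the trial.

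**What to change.** In both places (Trial design, and Secondary Effectiveness Endpoints, item 7) add a further condition to technical success: deployment of at least one Dragonfly-M device on the mitral valve. Report beside the rate the number of patients in whom no device was deployed. The count is needed even after the amendment, because a rate of 18/20 with deployment required could contain 0, 1 or 2 non-deployments.

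The cost is one clause in two places and one extra reported number. No visit, test or data item is added, because implantation status is already needed for acute procedural success. There are two drawbacks: the technical success rate may look less favourable, and the amended endpoint combines delivery-system failures with deployment failures. The reported count deals with the second.
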